2. STUDY OBJECTIVES

The objectives of this study are:

Primary objective:

1. To describe in routine clinical practice the effectiveness of the interferon-free ABBVIE REGIMEN ± RBV in patients with CHC as evidenced by sustained virological response at 12 weeks after end of treatment (SVR12)

Secondary objectives:

2. To provide real world evidence for predictive factors of virological response
3. To describe the pattern of real world use of the ABBVIE REGIMEN ± RBV with respect to different patient and treatment characteristics
4. To evaluate the influence of adherence on treatment outcome in routine clinical practice
5. To collect information on co-morbidities and concomitant medication in the Belgian population
6. To describe the tolerability of the ABBVIE REGIMEN ± RBV
7. To determine the impact of the ABBVIE REGIMEN ± RBV on healthcare resource utilization
8. To evaluate the contribution of the patient support program (PSP) to disease control, treatment continuation over time, patient satisfaction and PSP utilization
9. To assess viral resistance patterns

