- Other co-morbidities (every patient not reporting the respective co-morbidity is considered as not having the respective co-morbidity)
 - Depression (No [reference], Yes)

- Diabetes mellitus (No [reference], Type 1/Type 2)
 - Hypertension (No [reference], Yes)
 - Immunologically mediated disease (No [reference], Yes)
 - Hypothyroidism (No [reference], Yes)
 - Alcohol use (None [reference], Yes –occasional, Yes –regular, Exdrinker)
 - Key clinical chemistry and hematology laboratory variables at baseline
 - ALT ratio (continuous, see 4.2.6.5)
 - AST ratio (continuous, see 4.2.6.5)
 - Platelets [$10^9/L$] (continuous)
 - Prior treatment status (HCV treatment naïve [reference], HCV treatment experienced)

Additionally, an interaction term for cirrhosis status and genotype will be considered. If the most recent stage of liver fibrosis status (No cirrhosis/Transition to cirrhosis vs Cirrhosis), the genotype (G4, G1b vs G1a) or the interaction of both remains in the final model, then additional MLR might be considered for the subgroups concerned, taking into account the treatment regimen (e.g. in cirrhotic G1 patients: RBV vs no RBV and 12 wks vs 24 weeks).

The categories pre-specified above could be modified in the analyses if this is supported by the data (e.g. categories could be combined, if their impact on SVR12 is similar). Furthermore, continuous variables can be replaced by categorical variables.

Adherence

Adherence will be displayed for the CP by genotype and cirrhosis status and for the SP by treatment regimen and cirrhosis status. Summary statistics (n, mean, median, standard deviation [SD], and range) will be generated for continuous variable. Numbers and percentages of patients will be presented for categorical variables.

- Adherence to Abbvie regimen (% of target dose [adherence=cumulated number of pills taken /(initial prescribed number of pills x planned duration)])
 - >105%
 - >95%--<=105%
 - >80%--<=95%
 - >50%--<=80%
 - <=50%
- Adherence to ribavirin (% of target dose [adherence=cumulated dose taken /(initial prescribed dose x planned duration)])

- >105%
 - >95%-<=105%
 - >80%-<=95%
 - >50%-<=80%
 - <=50%
- Percentage of actual treatment duration in relation to the target duration of ABBVIE regimen taken
- Deviating duration of ABBVIE regimen
 - Early discontinuation (actual duration is shortened for more than 7 days)
 - Not deviated
 - Exceedance (actual duration is prolonged for more than 7 days)

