- Method used to document adherence (Interview, Diary)
- Percentage of actual days with treatment with RBV in relation to the planned duration
- Ribavirin earlier discontinued than ABBVIE regimen
- Initial dose of Ribavirin
 - 1000 mg/day
 - 1200 mg/day
 - XXX
- Cumulative dose of Ribavirin (g)
- Dose modifications/termination of RBV [in patients taking RBV, for a patient more than one dose modification and its main reason could be reported, but for each single reason the patient is counted only once] (Total number of patients with lower dose than highest previous dose [including patients who stopped the treatment earlier], Anemia, Nausea/Vomiting, Rash, Other [including patients who discontinued ABBVIE regimen earlier, but did not stop the RBV treatment before the ABBVIE regimen])

In addition to the summary statistics of the adherence variables, logistic regression analyses will be performed for the following adherence variables: "adherence to Abbvie regimen" in all patients of the CP, "adherence to ribavirin" in all patients of the CP taking RBV, each categorized as follows: >=95%, >80%-<=95%, <=80% to investigate the additional impact of overall treatment adherence on SVR12. The categories may be changed if they are sparsely filled. Adherence will be included as mandatory covariate in addition to the baseline explanatory variables already mentioned above. Also the same methods will be applied as described above.

An overview of Tables is given in Table 8.

Table 8 Overview of Outputs for Primary and Secondary Effectiveness Analysis

Output Title	Output Short Name	Analysis Population
Virological Response Rates by Genotype and Cirrhosis Status – CP/CPSFU - <country>	tvr_<c>_gc_cp	Core population/ Core population with sufficient follow-up data
Virological Response Rates by Genotype and Cirrhosis Status in Patients who Completed ABBVIE Regimen – CP/CPSFU - <country>	tvr_<c>_gc_cp_ARC	Core population/ Core population with sufficient follow-up data: patients who completed ABBVIE regimen
Virological Response Rates – NCP - <country>	tvr_<c>_ncp	Non-core population
Relapse Rates by Genotype and Cirrhosis Status – CP - <country>	trr_<c>_gc_cp	Core population
Non-Response Rates by Genotype and Cirrhosis Status – CP - <country>	tnrr_<c>_gc_cp	Core population
Non-Response Rates by Genotype and Cirrhosis Status in Patients who Completed ABBVIE Regimen – CP - <country>	tnrr_<c>_gc_cp_ARC	Core population: patients who completed ABBVIE regimen

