Impact of Patient and Disease Characteristics on SVR12 – CP - <country>	tis_<c>_cp	Core population
Adherence by Genotype and Cirrhosis Status - CP - <country>	tah_<c>_gc_cp	Core population
Adherence by Treatment Regimen and Cirrhosis Status - SP - <country>	tah_<c>_gc_sp	Safety population
Impact of Adherence to Abbvie Regimen on SVR12 – CP - <country>	tiaa_<c>_cp	Core population
Impact of Adherence to Ribavirin on SVR12 in patients taking RBV – CP - <country>	tiar_<c>_cp_RBV	Core population: patients taking RBV

The layouts of the tables mentioned above are provided in Part II of the SAP (Table Shells).

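### The exploratory ribavirin-adherence model for SVR12 leaves out DAA adherence, so early stopping of the whole regimen is counted as a ribavirin effect

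*SAP*

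**What the plan says.** Secondary objective 4 in SAP section 2 is "To evaluate the influence of adherence on treatment outcome in routine clinical practice". SAP 4.2.7.2.1 (Adherence) defines the two measures in the same form:

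- DAA regimen: "adherence=cumulated number of pills taken /(initial prescribed number of pills x planned duration".
- Ribavirin: "adherence=cumulated dose taken /(initial prescribed dose x planned duration".

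The DAA measure is modelled in the whole core population. The ribavirin measure is modelled "in all patients of the CP taking RBV, each categorized as follows": at least 95%, above 80% up to 95%, and 80% or less. The covariate rule is "Adherence will be included as mandatory covariate in addition to the baseline explanatory variables already mentioned above". The list it points back to, under SVR12 (Exploratory Analyses) in the same section, holds demographics, disease characteristics, type of institute, co-infections, co-morbidities, baseline laboratory values, prior treatment status and a cirrhosis-by-genotype interaction. It has no DAA adherence, actual DAA duration or early DAA stop.

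Table 8 gives the two analyses separate outputs. The ribavirin one (tiar_<c>_cp_RBV) is titled "Impact of Adherence to Ribavirin on SVR12 in patients taking RBV". Protocol 9.7.3.3 says only that logistic regression will be used for adherence and specifies no adjustment.

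**The concern.** Ribavirin is given with the DAAs. Low ribavirin adherence can arise in two ways: the patient cuts or stops ribavirin while the DAAs continue, or the patient stops the whole regimen. The SAP foresees both. It tabulates ribavirin stopped earlier than the DAA regimen, and it counts separately those who left the DAA regimen early without having stopped ribavirin first.

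The two groups can be expected to differ in SVR12 for reasons unrelated to ribavirin. The second group lost DAA exposure. Some of them stopped because of virological non-response or breakthrough, which SAP 4.2.5 lists as termination reasons. Those with no usable follow-up value are set to failure under SAP 4.2.3. The ribavirin model pools the two groups, and no baseline covariate can separate them.

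What is at stake is the reading of one table that serves secondary objective 4. Readers will take it as evidence on whether taking less ribavirin costs response, which is a different question from whether stopping all treatment does.

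**Working it through.** The documents give no figure for the adherence models, so there is nothing to reproduce. The check has a specification step and an illustration.

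**1. Where an early stopper lands.** Take a 12-week plan (84 days), full dosing until the stop, and everything stopped on day 28. Both measures equal 28/84 = 33%. The 80% limit is 0.80 × 84 = 67.2 days, so anyone who stops everything by day 67 is in the lowest ribavirin band and is equally low on DAA adherence.

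**2. Illustration with no ribavirin effect.** All inputs are assumptions; none is in the documents. SVR12 is 95% with full DAA intake, whatever the ribavirin intake. A share *r* of ribavirin patients reduces ribavirin only. A share *s* stops everything early, with SVR12 equal to *q*. Ribavirin adherence is taken at two levels (low band or not), without baseline covariates.

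- SVR12 in the low band = (r × 0.95 + s × q) / (r + s).
- Odds ratio = odds in the low band / (0.95/0.05 = 19).

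| s | r | q | SVR12, low band | Odds ratio |
|---|---|---|---|---|
| 4% | 15% | 50% | (0.1425 + 0.0200)/0.19 = 85.5% | 5.91/19 = 0.31 |
| 4% | 10% | 30% | (0.0950 + 0.0120)/0.14 = 76.4% | 3.24/19 = 0.17 |
| 2% | 20% | 70% | (0.1900 + 0.0140)/0.22 = 92.7% | 12.75/19 = 0.67 |
| 1% | 15% | 50% | (0.1425 + 0.0050)/0.16 = 92.2% | 11.8/19 = 0.62 |
| 0.5% | 15% | 50% | (0.1425 + 0.0025)/0.155 = 93.5% | 14.5/19 = 0.76 |

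The second and third rows are the extremes for s = 2-4%, r = 10-20% and q = 30-70%, so the range is 0.17-0.67. A separate calculation with SVR12 of 96% under full DAA intake, s = 2-6% and r = 5-20% gave 0.06-0.61.

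**3. With DAA adherence in the model.** The early stoppers get their own term. The ribavirin coefficient then compares ribavirin-only reducers with full adherers, 95% against 95%, and the odds ratio is 1.00 in every scenario.

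**4. What adjustment costs.** Take the first row with an assumed 250 ribavirin patients. There are 202.5 full adherers (10.125 expected failures), 37.5 ribavirin-only reducers (1.875) and 10 stoppers (5), or 17 failures in all.

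- Adjusted: the standard error of the log odds ratio is √(1/1.875 + 1/35.625 + 1/10.125 + 1/192.375) = 0.82. The 95% interval around 1.00 is about 0.20-4.9.
- Unadjusted: the low band has 6.875 failures in 47.5. The standard error is √(1/6.875 + 1/40.625 + 1/10.125 + 1/192.375) = 0.52. The interval around 0.31 is about 0.11-0.87.

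The unadjusted interval is narrower, but it is centred on the wrong value.

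**The case against.** **The SAP promises no ribavirin effect independent of the DAAs.** Its stated purpose is the added impact of overall treatment adherence, and the regressions are exploratory and data driven. This is fair: the output can be read as a crude association. But the table title names ribavirin alone, and nothing tells the reader that whole-regimen stopping is included.

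**The rule could mean both adherence measures enter each model.** No sentence excludes DAA adherence from the ribavirin model. The two populations, the separate categorisation and the two outputs point to one measure per model. If both were meant, the SAP needs to say so.

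**The size is assumed, and stopping may be rare.** Protocol 7.1 reports a low discontinuation rate in Phase III. This stands. At 1% or 0.5% stoppers with otherwise central inputs, the low band differs from 95% by less than 3 percentage points.

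**Other planned tables show the mixing.** Early discontinuation is tabulated, and response is repeated in patients who completed the DAA regimen. These tables would alert a careful reader, but they do not correct the regression.

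Three stronger readings are tempting and are not supported:

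- *A reader might infer that the problem exists whatever the adherence denominator.* It does not. With actual duration as denominator, a patient on full doses until the stop would score about 100% and stay out of the low band. The problem follows from the SAP's choice of planned duration.
- *A reader might infer that the study would declare a false ribavirin effect at a calculable rate.* The 0.05 threshold governs which covariates survive backward elimination. Adherence is forced into the model, so no declaration rule applies to it.
- *A reader might infer that the main effectiveness result is biased.* It does not use these models.

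**Conclusion.** The point holds for one exploratory analysis. As specified, the ribavirin odds ratio mixes reduced ribavirin with abandonment of the whole regimen and is biased toward an apparent ribavirin effect. The direction is firm provided that some ribavirin patients stop everything early and that they respond less often than patients who continue the DAAs. The termination reasons and the missing-equals-failure rule make the second condition likely.

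The size cannot be taken from the documents. The range of about 0.17-0.67 rests on the assumed shares and response rates shown above. With 1% or fewer early stoppers the bias is small at central inputs, although an odds ratio of 0.43 is still possible at 1% stoppers, 10% ribavirin-only reductions and 30% SVR12 in stoppers: (0.095 + 0.003)/0.11 = 89.1%, and 8.17/19 = 0.43. The primary SVR12 estimate and the DAA-adherence model are not affected. This is a worthwhile inexpensive improvement, not a threat to the study's main conclusion.

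**What to change.** 1. In SAP 4.2.7.2.1, state that the model behind tiar_<c>_cp_RBV includes adherence to the DAA regimen as a second mandatory covariate, with categories collapsed if sparse.
2. Add a cross-table of SVR12 (numerator and denominator) by DAA adherence and ribavirin adherence in core-population patients taking ribavirin.
3. If the two measures cannot be separated, repeat the ribavirin analysis in patients with DAA adherence of at least 95%. Label the unadjusted result as an association that includes whole-regimen discontinuation.
4. While editing, remove the overlap at exactly 95% between the two upper regression bands, since the restriction in item 3 uses that limit.

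The cost is a sentence or two in the SAP and one extra table. DAA adherence is already derived for the companion model and no new data are needed. The downside is a wider confidence interval for ribavirin, because failures are few and the two measures are correlated. The adjusted estimate may be too imprecise to support a conclusion, and the report should then say so.

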4.2.7.2.2 Attitude towards self-management, medication and support

The attitude towards self-management, medication and support will be analyzed for the CP.

Patient Support Program- (PSP)

The PSP utilization and satisfaction assessment will evaluate the frequency of utilization and patient's overall satisfaction with their respective Patient Support Program.

The contribution of the patient support program (PSP) to disease control, treatment continuation over time, patient satisfaction and PSP utilization will be analyzed using descriptive and

exploratory statistical methods. Frequency tables will summarize all corresponding variables of the PSP questionnaires over time stratified by cirrhosis status and treatment regimen.

PSP Utilization Questionnaire

- Participation in the Abbvie Patient Support Program (PSP)
 - Yes
 - No
- Utilization of any components from ABBVIE PSP since last visit (Yes, No)
- Personal support
- Educational and information material
 - Printed (Usually daily, Several times per week, Usually once a week, Less than once a week)
 - Online (Usually daily, Several times per week, Usually once a week, Less than once a week)
- Additional digital and mobile resources
 - Web-portal (Usually daily, Several times per week, Usually once a week, Less than once a week)
 - Reminders (SMS)

PSP Utilization and Satisfaction Questionnaire

- Participation in the Abbvie Patient Support Program (PSP)
 - Yes
 - No
- Utilization of any components from ABBVIE PSP since last visit
 - No
 - Yes
 - Satisfaction in general (Very good, Good, Satisfactory, Poor)
 - Satisfaction (Very good, Good, Satisfactory, Poor)
 - Address needs(Yes, fully, Yes, mostly, No)
- Personal support (Very good, Good, Satisfactory, Poor)

- Educational and information material
 - Printed
 - Frequency of Usage (Usually daily, Several times per week, Usually once a week, Less than once a week)
 - Satisfaction (Very good, Good, Satisfactory, Poor)
 - Online
 - Frequency of Usage (Usually daily, Several times per week, Usually once a week, Less than once a week)
 - Satisfaction (Very good, Good, Satisfactory, Poor)
- Additional digital and mobile resources
 - Web-portal
 - Frequency of Usage (Usually daily, Several times per week, Usually once a week, Less than once a week)
 - Satisfaction (Very good, Good, Satisfactory, Poor)
 - Reminders (SMS): Satisfaction (Very good, Good, Satisfactory, Poor)

No imputation will be performed for missing items.

In addition, univariate and multiple logistic regression (MLR) analysis will be performed to investigate the association of the use of the PSP, the patient satisfaction variables of the PSP questionnaires with treatment completion. First the use of PSP will be analyzed in all CP patients. The patient satisfaction will only be analyzed in patients who participated in the PSP. The satisfaction categories pre-specified above could be combined in the analyses if this is supported by the data (e.g. very good and good vs satisfactory vs poor). Furthermore, continuous variables can be replaced by categorical variables.

Use of the PSP is defined as taking part in PSP. For all satisfaction variables the worst case before last intake is considered. 'Poor' will be used as reference value. Patients will be considered to have completed treatment when the actual duration of the ABBVIE REGIMEN is not shortened for more than 7 days.

If the percentage of patients with available data for a variable is lower than 80% of the patient group analyzed, then this variable will not be considered in the MLR analysis.

These analyses will be of exploratory nature and data driven. Backward selection procedures will be applied to generate the final MLR models. A p-value <0.05 will be used for the covariates to stay in the model in a backward elimination step.

Patient Activation Measure – (PAM-13)

The Patient Activation Measure (PAM) 13 is a measure used to assess the patient knowledge, skill, and confidence for self-management. The PAM-13 item scale is a measure used to assess the patient knowledge, skill, and confidence for self-management. Each of the 13 items can be answered with one of four possible response options, which are “disagree strongly” (1), “disagree” (2), “agree” (3), “agree strongly” (4).

The scoring will be done by Insignia Health. If there are less than nine items answered, no summary score will be calculated.

A summary table will show descriptive statistics (n, mean, median, SD, minimum and maximum) of the score for baseline and the post-baseline time points, as well as changes from baseline, by cirrhosis status and treatment regimen. In addition, analysis of covariance (ANCOVA) will be applied to investigate the effect of the different ABBVIE REGIMENS (\pm RBV) by cirrhosis status on the score using the corresponding baseline value as covariate.

Beliefs Medication Questionnaire – (18-item BMQ)

The 18-item BMQ consists of 18 questions used to screen for patients' beliefs, attitudes and concerns about their medication. The BMQ consists of two sections, the BMQ-Specific and the BMQ-General. The BMQ-Specific section comprises two 5 item subscales assessing the necessity of and the concerns about the prescribed medication for personal use (Specific-Necessity and Specific-Concerns). The BMQ-General section comprises two 4 item subscales assessing beliefs that medicines are harmful and overused by doctors in general (General-Harm and General-Overuse). The 18 items are rated on a Likert scale from 1=strongly disagree to 5 = strongly agree and the 18 items are summarized into the 4 subscale scores. The total score of each BMQ subscale will be calculated.

If for any of these subscales one single item is missing, the subscale will be calculated as the mean of the remaining items. This corresponds to replacing the missing value by the “average” of the available answers. If more than one item is missing, the respective subscore will be considered as not evaluable.

A summary table will show descriptive statistics (n, mean, median, SD, minimum and maximum) of the four scores for baseline and the post-baseline time points, as well as changes from baseline, by cirrhosis status and treatment regimen. In addition, analysis of covariance (ANCOVA) will be applied to investigate the effect of the different ABBVIE REGIMENS (\pm RBV) by cirrhosis status on BMQ endpoints using the corresponding BMQ baseline values as covariates.

Table 9 Overview of Outputs for Secondary Variables

Output Title	Output Short Name	Analysis Population
PAM-13 by Treatment Regimen and Cirrhosis Status - CP - <country>	tpam_<c>_tc_cp	Core population
BMQ by Treatment Regimen and Cirrhosis Status - CP - <country>	tbmq_<c>_tc_cp	Core population
PSP Utilization Until 12 weeks after EoT in Patients Taking Part in PSP by Treatment Regimen and Cirrhosis Status - CP - <country>	tpspu_<c>_tc_cp_ps p	Core population: Patients Taking Part in PSP
PSP Utilization and Satisfaction Until 12 weeks after EoT in Patients Taking Part in PSP by Treatment Regimen and Cirrhosis Status - CP - <country>	tpspu_<c>_tc_cp_ps p	Core population: Patients Taking Part in PSP
Impact of PSP on Treatment Completion - CP - <country>	tptc_<c>_cp	Core population

The layouts of the tables mentioned above are provided in Part II of the SAP (Table Shells).

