### **9.7.5 PSP, PAM and BMQ**

The contribution of the patient support program (PSP) to disease control, treatment continuation over time, patient satisfaction and PSP utilization will be analyzed using descriptive and exploratory statistical methods. Appropriate frequency tables will summarize all corresponding variables of the PSP questionnaire (see ANNEX 3 and 4) over time stratified by ABBVIE REGIMEN arms. In addition, multiple logistic regression (MLR) analysis will be performed to investigate the association between the use of the PSP and the patient satisfaction variables of the PSP questionnaire with the probability to treatment completion. These MLRs will be performed similar to the MLRs for SVR12 (see Section 9.7.3.3. Additional details will be specified in the SAP.

The Patient Activation Measure (PAM) 13 item scale is a measure used to assess the patient knowledge, skill, and confidence for self-management. Each of the 13 items can be answered with one of four possible response options, which are “disagree strongly” (1), “disagree” (2), “agree” (3), “agree strongly” (4).

Based on responses to the 13-item measure, the score is calculated by adding up the raw scores (range of the sum: 13 – 52) and mapping up the value onto a scale of 0–100 indicating strength of agreement with the 13 items  $(100 *(\text{sum} - 13) / (52 - 13))$ . The final score can be assigned to one of the four levels of activation. A higher score indicates that the patient is likely to participate more actively in health care processes and takes more responsibility for his or her health.

In case of missing item values, the mean value of the available items will be used for replacement. However, if there are less than nine items answered, no summary score will be calculated.

A summary table will show descriptive statistics (n, mean, median, SD, minimum and maximum) for the summary score at baseline and the post-baseline time points, as well as changes from baseline. In addition analysis of covariance (ANCOVA) will be applied to investigate the effect of the different ABBVIE REGIMENS ( $\pm$  RBV and duration) on the summary score using the corresponding baseline value as covariates. Further details will be specified in the SAP.

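### The SAP names no adjustment for the regression of treatment completion on patient support program use and lets backward elimination remove PSP use, so the only assured estimate is the crude one

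*SAP*

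**What the plan says.** Evaluating what the PSP contributes to treatment continuation is a secondary objective (Protocol 8.2.2, SAP 2). SAP 4.2.7.2.2 addresses it by univariate and multiple logistic regression of the "association of the use of the PSP, the patient satisfaction variables of the PSP questionnaires with treatment completion". Two populations are set: "First the use of PSP will be analyzed in all CP patients", and "The patient satisfaction will only be analyzed in patients who participated in the PSP". PSP use is one yes/no variable, participation. Completion means that the regimen was not cut short by more than 7 days. "Backward selection procedures will be applied to generate the final MLR models", with p<0.05 needed to stay, and PSP use is not exempted. No demographic, disease or treatment covariate is named.

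Four other places bear on this:
- Protocol 9.7.5: "These MLRs will be performed similar to the MLRs for SVR12", with further detail left to the SAP.
- SAP 4.2.7.2.1, adherence model: "Adherence will be included as mandatory covariate in addition to the baseline explanatory variables already mentioned above".
- SAP 4.2.7.2.2, descriptive part: frequency tables of the "PSP questionnaires over time stratified by cirrhosis status and treatment regimen".
- SAP Table 9 lists one output on the impact of the PSP on treatment completion in the core population (CP). Its layout is in Part II, which is not among the documents.

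**The concern.** Nothing in the documents suggests that PSP participation is allocated by design, so participants and non-participants may differ in ways that also affect whether they finish treatment. Ribavirin is a plausible example: Protocol 7.1 attributes many adverse events and laboratory abnormalities to it. Cirrhosis is another. Protocol 9.9 names uncontrolled confounding as a limitation and recording the common confounders as a way to increase validity. This model names none of them.

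The selection rule adds a second problem. In a model built to answer a question about one exposure, that exposure should not have to earn its place by p-value. If PSP use is eliminated, the final multiple model says nothing about it, and what remains is the unadjusted result in a table presented as the program's impact. A PSP with no effect could then look helpful or harmful because of who joined.

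**Working it through.** **1. What the all-CP model can contain.** Satisfaction is analysed only in participants, so it cannot enter a model that compares participants with non-participants. That leaves PSP use as the only named candidate. The multiple model then either repeats the univariate model (PSP use stays) or is empty (PSP use is removed).

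**2. Whether the protocol's link to the SVR12 models fills the gap.** The SVR12 covariate list in SAP 4.2.7.2.1 includes cirrhosis, itself removable by elimination. It does not include ribavirin or planned duration. These appear only in subgroup models that might follow. Importing the list would therefore give one of the main adjusters, unprotected, and would still not protect PSP use.

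**3. How often PSP use would survive p<0.05.** N = 417 is the evaluable CP size in SAP 3.2. The plan gives no power or effect size for this regression, so the rest is assumed: uptake 30 to 70%, non-completion among non-users (p0) 2 to 10%, and a true odds ratio for non-completion of 0.5 or 0.67. A two-sided comparison of two proportions approximates the stay criterion.

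Example with p0 = 5%, uptake 50% (208.5 per group) and odds ratio 0.5:
- Odds in users = 0.5 × 0.05/0.95 = 0.0263, so p1 = 0.0256. The difference is 0.0244 and the pooled proportion 0.0378.
- SE under no difference = √(0.0378 × 0.9622 × 2/208.5) = 0.0187.
- SE under the alternative = √((0.05 × 0.95 + 0.0256 × 0.9744)/208.5) = 0.0186.
- z = (0.0244 − 1.96 × 0.0187)/0.0186 ≈ −0.66, so the chance of staying is about 0.25.

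Over the whole range the chance is about 8 to 45% for odds ratio 0.5 (about 6 to 36 non-completers) and about 5 to 20% for 0.67. Removal is the likelier outcome throughout, even when the program works.

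**4. How far the crude odds ratio could be off with no true PSP effect.** Let a confounder be present in a share q1 of users and q0 of non-users, with non-completion risk r1 with it and r0 without it. Then a = q1·r1 + (1−q1)·r0, b = q0·r1 + (1−q0)·r0, and the crude odds ratio is [a/(1−a)]/[b/(1−b)].

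Example with ribavirin in 60% v 40%, r0 = 3%, r1 = 9%: a = 0.054 + 0.012 = 0.066; b = 0.036 + 0.018 = 0.054; odds ratio = (0.066/0.934)/(0.054/0.946) = 1.24.

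| Assumed share, users v non-users | r0/r1 2%/4% | 3%/9% | 3%/12% |
|---|---|---|---|
| Ribavirin 55% v 45% | 1.07 | 1.11 | 1.14 |
| Ribavirin 60% v 40% | 1.15 | 1.24 | 1.30 |
| Ribavirin 70% v 30% | 1.32 | 1.54 | 1.70 |
| Cirrhosis 25% v 20% | 1.04 | 1.08 | 1.10 |
| Cirrhosis 40% v 20% | 1.17 | 1.30 | 1.40 |
| 24 weeks 8% v 2% | 1.06 | 1.12 | 1.18 |
| 24 weeks 10% v 0% | 1.10 | 1.21 | 1.31 |

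Swapping users and non-users gives the reciprocals, so the bias can run either way. The 24-week rows rest on Protocol 9.7.7, which expects about 95% of the interim set to receive 12 weeks. At equal uptake both splits average 5% on 24 weeks.

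**5. Bias against imprecision.** With 417 patients, uptake 50%, no effect and non-completion of 5%, there are 417 × 0.05 = 20.85 non-completers, about 10.4 per group, and 198.1 completers per group. SE of the log odds ratio = √(2/10.4 + 2/198.1) = 0.45, so the 95% CI around 1 is about 0.41 to 2.41. At 2% non-completion it is about 0.25 to 3.94, and at 10% about 0.53 to 1.90.

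**The case against.** The strongest reply has four parts.

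- **An estimate does survive.** A univariate regression of PSP use in all CP patients is planned and an output table is listed. This stands: elimination affects only the final multiple model. But the surviving estimate is the unadjusted one.
- **The SAP does not expressly limit the model to PSP variables.** The protocol ties these models to the SVR12 models. The SAP paragraph also speaks of continuous variables, although none of the PSP items it lists is continuous. This stands as far as it goes: the covariate set is unstated, not restricted. It does not rescue the plan, because the SVR12 list lacks ribavirin and duration. Where the SAP does want the baseline list carried over, in the adherence model, it says so.
- **The sizes are assumed.** True. Modest imbalances give odds ratios of about 1.04 to 1.14, which are small beside the intervals in step 5. Planned duration is probably a weak confounder if about 95% on 12 weeks holds for the whole study.
- **The analysis is exploratory and events will be few.** Both points are fair. The first lowers the stakes but does not justify letting the exposure drop out. The second limits how many covariates the model can carry, above all in the participant-only satisfaction models.

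**Conclusion.** The point holds in a limited form. The SAP names no covariate beyond the PSP variables, does not protect PSP use from elimination, and treats its adherence exposure differently without giving a reason. The only assured estimate for this objective is therefore crude, and open to confounding by ribavirin and cirrhosis.

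Three stronger readings are not supported. A reader might infer that no estimate or interval will be reported; the planned univariate analysis contradicts that. A reader might infer that the SAP confines the model to PSP variables; that is an inference from silence. A reader might infer that the result will be materially biased. The documents give no uptake, completion rate or imbalance from which to judge it, and the odds ratios of 1.04 to 1.70 (or their reciprocals) depend wholly on the assumed inputs. The retention chances of about 5 to 45% likewise rest on assumed effects and rates with N = 417.

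The primary SVR12 analysis is unaffected. This is a worthwhile, inexpensive change to an exploratory model that serves a stated secondary objective.

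**What to change.** In SAP 4.2.7.2.2, for the model in all CP patients:
- Keep PSP use as a mandatory covariate whatever its p-value, as the adherence model does for adherence.
- Adjust for ribavirin (yes/no) and cirrhosis (yes/no). Add planned duration (12 or 24 weeks) if enough patients are on 24 weeks.
- Report the crude and adjusted odds ratios side by side with 95% CIs.
- Use Firth penalised likelihood if non-completers are few.

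Adjustment of the participant-only satisfaction models should be optional and depend on the number of events.

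The cost is SAP wording and a small amount of programming, with no new data collection. The SAP already uses regimen and cirrhosis status for its PSP tables and planned duration for its adherence calculation. SAP 6.1 does not name PSP participation, completion or planned duration among its examples of derived variables, so their availability in the analysis data set needs checking. The statistical price is a wider interval, which could be appreciable with few non-completers. That is why the adjustment set should stay this short.
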